**Secondary Efficacy**

Similar to the primary endpoint analyses, pairwise comparisons will be performed using CMH tests stratified by analysis center. The secondary efficacy endpoints will be:

- Percentage of subjects who show at least a 2 grade improvement and reach Clear to Almost Clear at Week 12 for IDP-122 Lotion versus IDP-122 Vehicle Lotion
- Percentage of subjects who show at least a 2 grade improvement and reach Clear to Almost Clear at Week 6 for IDP-122 Lotion versus IDP-122 Vehicle Lotion
- Percentage of subjects who show at least a 2 grade improvement and reach Clear to Almost Clear at Week 4 for IDP-122 Lotion versus IDP-122 Vehicle Lotion
- Percentage of subjects who show at least a 2 grade improvement and reach Clear to Almost Clear at Week 2 for IDP-122 Lotion versus IDP-122 Vehicle Lotion

Evaluation of the secondary efficacy variables will use a gated sequential procedure starting with the comparisons of the first bulleted item and proceeding onto the next item. The process will terminate if a nonstatistically significant value is observed.

**Tertiary Efficacy**

The following tertiary efficacy endpoints will be analyzed to further characterize the treatment effect of IDP-122 Lotion over the IDP-122 Vehicle Lotion. The analyses will use CMH testing stratified by analysis center without adjusting for multiplicity.

- Percentage of subjects with at least a 2-grade improvement from Baseline in the score for each of the signs of psoriasis (erythema, plaque elevation, and scaling) at Week 8 for the target lesion
- Percentage of subjects with at least a 2-grade improvement from Baseline in the score for each of the signs of psoriasis (erythema, plaque elevation, and scaling) at Week 12 for the target lesion
- Percentage of subjects with at least a 2-grade improvement from Baseline in the score for each of the signs of psoriasis (erythema, plaque elevation, and scaling) at Week 6 for the target lesion
- Percentage of subjects with at least a 2-grade improvement from Baseline in the score for each of the signs of psoriasis (erythema, plaque elevation, and scaling) at Week 4 for the target lesion
- Percentage of subjects with at least a 2-grade improvement from Baseline in the score for each of the signs of psoriasis (erythema, plaque elevation, and scaling) at Week 2 for the target lesion

***Safety:***

Subjects will be assessed for the occurrence of new and ongoing AEs. Descriptions of AEs will include the dates of onset and resolution (if resolved), maximum severity, seriousness, action taken regarding the study drug, corrective treatment, outcome, and investigator's assessment of causality. All AEs will be recorded and classified using terminology from the Medical Dictionary for Regulatory Activities (MedDRA). All reported treatment-emergent AEs (TEAEs), defined as any AE with an onset on or after the date of first study drug application, will be summarized by treatment group, the number of subjects reporting TEAEs, system organ class, preferred term, severity, and relationship to study drug. When summarizing TEAEs by severity or relationship to study drug, each subject will be counted only once within a system organ class or a preferred term using the event with the greatest severity or causality, respectively, within each category. All reported serious adverse events (SAEs) will be summarized by treatment group, the number of subjects reporting SAEs, system organ class, preferred term, severity, and relationship to study drug.

All information pertaining to AEs noted during the study will be listed by subject and will include a verbatim description of the event as reported by the investigator, as well as the preferred term, system organ class, start date, stop date (if stopped), seriousness, severity, action taken regarding the study drug, corrective treatment, outcome and relationship to the study drug. In addition, a listing of subjects who prematurely discontinue from the study due to AEs will be provided as well as a listing of subjects who reported an SAE.

The frequency of local skin reactions including itching, dryness, burning/stinging, skin atrophy, striae, telangiectasia and folliculitis will be summarized by treatment group and visit. Additionally, the percent of subjects who experience a local skin reaction (itching, dryness, burning/stinging) graded at a level of 3, at any point in the study following the first application of study drug, will be tabulated by treatment group. Changes from baseline in safety laboratory values and vital sign measurements will be summarized with descriptive statistics for each treatment group at all applicable study visits.

Shift tables will be presented for changes in safety laboratory values to summarize laboratory test results collected at Baseline and Weeks 4 and 8. Normal ranges established by the central laboratory will be used to determine the shifts. A listing of all out-of-range laboratory test results at any assessment time point will also be provided. Determination of clinical significance for all out-of-range laboratory values will be made by each investigator and included in the listing. In addition, a listing of all clinically significant laboratory test results will be provided.

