**Statistical methods:**

All subjects who are randomized and dispensed study drug will be included in the intent-to-treat (ITT) analysis set. All subjects in the ITT analysis set who complete the Week 8 visit without any major protocol violations will be included in the per protocol (PP) analysis set. All subjects who are randomized, receive at least 1 confirmed dose of study drug, and have at least 1 post-baseline assessment will be included in the safety analysis set.

The ITT analysis set will be considered primary for the evaluation of efficacy. The primary method of handling missing efficacy data will be the method of Markov Chain Monte Carlo (MCMC) multiple imputation; no imputations will be made for missing safety data.

*Efficacy:*Efficacy Endpoints

The efficacy endpoints are intended to compare once daily application of IDP-122 Lotion and vehicle. Specifically, the efficacy endpoints include:

- The percent of subjects with treatment success, defined as at least a 2 grade improvement from Baseline in the IGA score and an IGA score equating to “clear” or “almost clear” at Weeks 2, 4, 6, 8 and Week 12 (4-week follow-up), as summarized using descriptive statistics.
- The percent of subjects with at least a 2-grade improvement from Baseline in the score for each of the signs of psoriasis (erythema, plaque elevation, and scaling) at Weeks 2, 4, 6, 8 and Week 12 (4 week FU), as summarized using descriptive statistics for the target lesion treated with study drug.

Inferential Statistics**Primary Efficacy**

The primary efficacy endpoint will be the percent of subjects with treatment success, defined as at least a 2-grade improvement from Baseline in IGA score and an IGA score equating to “Clear” or “Almost Clear”. The primary efficacy endpoint will be used to compare once daily application of IDP-122 Lotion with its vehicle. The percent of subjects with treatment success at Week 8 will be analyzed using Cochran-Mantel-Haenszel (CMH) tests stratified by analysis center.

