## **11.5 Adverse Events**

### **11.5.1 Definition of Adverse Event**

An AE is any untoward medical occurrence in a patient or clinical investigation subject administered a medicinal product and which does not necessarily have a causal relationship with the study drug. AEs include any unfavorable and unintended illness, sign, symptom, clinically significant laboratory test abnormality, or disease temporally associated with the use of a medicinal product that has appeared or worsened during the course of the clinical trial, regardless of causal relationship to the study drug(s) under study. The collection of nonserious AEs and serious adverse events (SAEs) should begin following the subject's completion of the consent process to participate in the study.

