### 11.5.2 Documenting Adverse Experiences

It is the responsibility of the investigator to document all AEs that occur during the course of the study. The AEs should be documented as a single medical diagnosis. When this is not possible, the AE should be documented in terms of signs and/or symptoms observed by the investigator or reported by the subject at each study visit.

All AEs occurring after the subject signs the informed consent through the last study visit must be reported, regardless of whether or not the AEs are considered drug-related. All AEs, whether in response to a query, observed by the study site personnel, or reported spontaneously by the subject, will be recorded.

At each visit during the study, the subject will be assessed for the occurrence of new and ongoing AEs. Cutaneous tolerability signs and symptoms that result in the subject's requiring a concomitant therapy or discontinuation from the study will be reported as an AE. The following data will be collected on all AEs and recorded on the appropriate eCRF:

- Event name (diagnosis preferred, if unknown, record the signs/symptoms)
- Onset date and end date
- Maximum intensity (severity)
- Seriousness
- Action taken regarding study drug
- Corrective treatment, if given
- Outcome

In addition, the investigator's assessment of causality will be recorded.

Vital sign abnormalities are to be recorded as AEs only if they are clinically significant (for example: are symptomatic, requiring corrective treatment, leading to discontinuation or fulfilling a seriousness criterion).

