## **12.2 Assessment of Safety**

### **12.2.1 Adverse Events**

The primary analysis of safety will be conducted at Week 8. There will be a tabulation, however, of the AE's that start in the period post the Week 8 to Week 12 visit. All AEs occurring during the study will be recorded and classified using terminology from the Medical Dictionary for Regulatory Activities (MedDRA). All reported treatment-emergent adverse events (TEAEs), defined as any AE with an onset on or after the date of first study drug application, will be summarized by treatment group and will provide the number of subjects reporting TEAEs, system organ class, preferred term, severity, and relationship to study drug. When summarizing TEAEs by severity or relationship to study drug, each subject will be counted only once within a system organ class or a preferred term using the event with the greatest severity or causality, respectively, within each category. All reported SAEs will be summarized by the number of subjects reporting the event, system organ class, preferred term, severity, and relationship to study drug.

All information pertaining to AEs noted during the study will be listed by treatment group and subject and will include a verbatim description of the event as reported by the investigator, as well as the preferred term, system organ class, start date, stop date (if stopped), seriousness, severity, action taken regarding the study drug, corrective treatment, outcome, and relationship to the study drug. In addition, a listing of subjects who prematurely discontinue from the study due to AEs will be provided as well as a listing of subjects who reported an SAE.

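### The SAE summary has no onset limit, so SAEs from screening in subjects later treated are counted in a treatment arm

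*Combined protocol and SAP*

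**What the plan says.** The safety part of the synopsis limits the AE tables to TEAEs, "defined as any AE with an onset on or after the date of first study drug application". The rule for serious events is different: "All reported serious adverse events (SAEs) will be summarized by treatment group", broken down further by MedDRA class and term, severity and relationship to study drug. It gives no onset condition.

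Section 12.2.1 repeats the pattern. TEAEs are restricted by onset, while "All reported SAEs will be summarized by the number of subjects reporting the event, system organ class, preferred term, severity, and relationship to study drug". That sentence does not mention treatment group, so the by-arm presentation rests on the synopsis.

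Collection starts well before treatment. Section 11.5.2 requires that "All AEs occurring after the subject signs the informed consent through the last study visit must be reported", and Section 11.5.1 also starts collection of serious and nonserious events after consent. Section 11.1.1 places Screening between Day -35 and Day -1. Section 12.8.1 runs the safety analyses on subjects who were randomized, had at least one confirmed dose and had at least one safety assessment after Baseline.

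**The concern.** Within one section of the plan, two neighbouring tables use different time windows. The TEAE table starts at the first application and the SAE table starts at consent. Nothing suggests that this is deliberate. The tabulation of grade 3 local skin reactions, in the synopsis and in Section 12.2.2, is also limited to the time after the first application, so the SAE summary is the exception. No separate table of treatment-emergent SAEs is described.

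The SAE table is among the first safety results a reader looks at, and its counts are likely to be small. One event that cannot be due to treatment can change how an arm's row reads. The relationship column has no meaning for an event before the first application. A reader who tries to match the serious events in the TEAE output with the SAE table may find that they disagree, with no explanation in the plan.

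**Working it through.** The plan gives no SAE figure to reproduce. Its only design calculation, power above 95% with 140 and 70 subjects (Section 12.8.2), reproduces at 98.0% with Fisher's exact test. It is not affected by this point.

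**Tracing one event.** Take an SAE with onset at Day -20.

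1. It falls after consent, so Sections 11.5.1 and 11.5.2 require it to be collected.
2. If the subject stays eligible, Section 11.1.2 has the subject randomized at Baseline and applying the first dose at the center that day.
3. After one later safety assessment the subject is in the safety set (Section 12.8.1).
4. TEAE test: Day -20 is before Day 0, so the event is not in the TEAE table.
5. SAE test: the event was reported, so it is in the SAE table, in the column of the assigned arm and under a causality category.

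**Size of one event.** 1/140 = 0.7% of the IDP-122 arm; 1/70 = 1.4% of the vehicle arm.

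**Share of SAEs before application.** Assume a constant SAE rate over s screening days and the 84 days from Day 0 to Week 12. The share is s/(s + 84):

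- s = 1: 1/85 = 1.2%
- s = 14: 14/98 = 14.3%
- s = 28: 28/112 = 25.0%
- s = 35: 35/119 = 29.4%

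Screening of 14 to 28 days is plausible for some subjects. Sections 8.2 and 9.4 require washouts of 14 days (topical antipsoriatics) and 4 weeks (phototherapy and non-biologic systemic therapy), and Section 11.1.1 schedules Baseline after washout.

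**Expected counts.** The documents give no SAE rate. Assume 2 to 8 per 100 person-years and 210 subjects. Expected count = 210 × days/365.25 × rate; chance of at least one = 1 − exp(−expected).

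| Period | Person-years | Expected SAEs | Chance of at least one |
|---|---|---|---|
| 14 screening days | 8.05 | 0.16 to 0.64 | 15% to 47% |
| 35 screening days | 20.12 | 0.40 to 1.61 | 33% to 80% |
| 84 days from Day 0 | 48.30 | 0.97 to 3.86 | not needed |

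With 2:1 allocation, the 35-day row splits into 0.27 to 1.07 expected events in the IDP-122 arm and 0.13 to 0.54 in the vehicle arm. The expected number per subject is the same in both.

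These counts are upper bounds for each screening length. They give every subject that length and assume that every subject with a screening SAE is still randomized.

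**The case against.** The strongest reply is that the effect is small and visible. Screening SAEs occur before randomization, so their expected rate per subject is equal in the two arms, and no safety hypothesis test is planned. All AEs are listed by subject with start date and seriousness, and a further listing covers subjects with an SAE, so a Day -20 event can be recognized. Eligibility, including general health, is checked again at Baseline, so some of these subjects would never be randomized. SAEs in subjects who are never treated do not reach an arm at all. Tabulating everything after consent could also be a deliberate, inclusive choice.

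Most of this stands, and it limits the size of the point. It does not remove it. A listing lets a careful reader undo the count, but the table remains the summary that is read and cited. If inclusiveness was intended, the plan should say so and show the two periods apart.

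A reader might also infer that the statement "no imputations will be made for missing safety data" pushes AEs with an incomplete onset date out of every TEAE table. The documents do not support that. No section excludes such events. Some partial dates settle the matter without imputation, for example a known month later than that of the first application. An undated SAE would still be tabulated, because the SAE summary takes all reported events. Their classification is undefined, and that is a date convention for the separate SAP to which Section 12 defers.

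**Conclusion.** The point holds on the wording. If the plan is followed exactly, SAEs from before the first application in subjects of the safety set are counted by arm and by relationship to study drug. The effect is non-treatment events in very small counts and an SAE table that does not match the TEAE table.

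A reader might infer that this biases the safety comparison for or against IDP-122. It does not in expectation: the events precede randomization, so the expected difference between the arm percentages is the same with or without them.

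The size of one event, 0.7% or 1.4% of an arm, follows from the planned arm sizes alone. The share of up to about 29% rests on a constant rate and a full 35-day screening. The 33% to 80% chance of at least one such event also rests on an SAE rate that the documents do not give, and should be read as an illustration. This is a clarification worth making before unblinding. It does not threaten the trial's conclusions.

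**What to change.** In the safety part of the synopsis and in Section 12.2.1, replace the SAE sentence with wording to this effect: *Treatment-emergent SAEs (onset on or after the date of first application) will be summarized by treatment group. SAEs with onset before that date will be listed separately.* Naming treatment group in Section 12.2.1 also brings it into line with the synopsis, and the separate SAP should carry the same rule.

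The cost is a sentence in each place and one filter in the SAE program. The only loss is that SAEs before the first application move from a table to a listing, where they remain fully reported. Data collection, sample size and power do not change.

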**Sample size calculations:**

One hundred forty (140) IDP-122 treated subjects and seventy (70) vehicle treated subjects will have greater than 95% power to detect a statistically significant outcome for a two-sided test with an alpha level of 0.05. This is based on treatment success rates of 33.3% and 9.7% which were observed in V01-118A-201. Success was defined as at least a 2-grade improvement from Baseline in the IGA score and an IGA score equating to "Clear" or "Almost Clear".

This study will be performed in compliance with GCP including the archiving of essential study documents. This protocol follows guidelines outlined by the International Conference on Harmonization (ICH). All data furnished to the investigator and his/her staff, and all data obtained through this study, will be regarded as confidential and proprietary in nature and will not be disclosed to any third party, except for the United States Food and Drug Administration or other regulatory body, without written consent from the sponsor.

## 4 List of Abbreviations and Definitions of Terms

Abbreviation or Specialist Term	Definition or Explanation
AE	Adverse event
BSA	Body surface area
CBC/Diff	Complete blood count with differential
CMH	Cochran-Mantel-Haenszel
eCRF	Electronic Case Report Form
DLQI	Dermatology Life Quality Index questionnaire
ET	Early termination
FDA	United States Food and Drug Administration
GCP	Good Clinical Practice
HP	Halobetasol propionate
ICH	International Conference on Harmonization
IEC	Independent Ethics Committee
IGA	Investigator's Global Assessment
IRB	Institutional Review Board
ITT	Intent-to-treat
LOCF	Last observation carried forward
MCMC	Markov Chain Monte Carlo
MedDRA	Medical Dictionary for Regulatory Affairs
PP	Per protocol
SAE	Serious adverse event
TEAE	Treatment-emergent adverse event

In this protocol, “sponsor duties” refer to responsibilities that will be performed by the sponsor, the sponsor’s designee, or the sponsor’s designated contract research organization. In this protocol, “investigator” refers to the principal investigator or his/her designee, who is responsible for performing the study procedures and assessments.

## 5 Introduction

Psoriasis is a chronic, immune-mediated disease that varies widely in its clinical expression. Disease severity ranges from mild (limited number of plaques) to very severe. Characteristic features of psoriasis include hyperproliferation of epidermal cells associated with dermal/epidermal inflammation, resulting in sharply demarcated red plaques, which may be covered by silvery scales affecting the skin and scalp.

There are presently no curative treatments for psoriasis. Treatment options focus on relieving symptoms, reducing inflammation, induration, and scaling, and controlling the extent of the disease. Patient age, severity of disease, and the type and extent of body surface area (BSA) involvement are considerations in selecting therapy.

Biologic treatments are now either available or in development to treat psoriasis. However, these treatments are not typically used for mild disease, and their safety profile is not entirely well understood.

Topical therapies are used in all disease severities, but may be impractical when psoriasis involves a large BSA. The mainstay of psoriasis treatment is topical corticosteroids, which range in potency from superpotent to low potency (Class I to Class VII, respectively). Generally, the more potent corticosteroids are required for effective management of psoriasis.

Although topical corticosteroids are very effective, long-term safety remains a concern, particularly with the more potent ones. Adverse effects such as skin atrophy, telangiectasia, and potential hypothalamic-pituitary-adrenal axis suppression have been associated with higher potency topical corticosteroids and prolonged treatment. Ultravate® cream and ointment (halobetasol propionate [HP] 0.05%) is currently on the market and are classified as super-high potency (Class I) corticosteroids indicated for the relief of the inflammatory and pruritic manifestations of corticosteroid-responsive dermatoses.

Having a lower concentration product that is a Class I steroid might be advantageous for patients, as the steroid provides relief from inflammation, and may reduce the adverse reactions associated with a steroid (eg, skin atrophy).

## 6 Study Objectives and Purpose

The objective of the study is to evaluate the safety and efficacy of topical IDP-122 Lotion when applied once daily to adult subjects with moderate to severe plaque psoriasis (defined as an Investigator's Global Assessment [IGA] score of 3 or 4). The intent of the study is specifically to evaluate the safety and efficacy of a once daily application of IDP-122 Lotion in comparison with vehicle.

